# Introduction

## Background and rationale

Neck and shoulder complaints are common in primary care physiotherapy. These patients experience pain and disability, resulting in high societal costs due to, for example, healthcare use and work absence. Content and intensity of physiotherapy care can be matched to a patient's risk of persistent disabling pain. Mode of care delivery can be matched to the patient's suitability for blended care (integrating eHealth with physiotherapy sessions). It is hypothesized that combining these two approaches to stratified care (referred to from this point as Stratified Blended Approach) will improve the effectiveness and cost-effectiveness of physiotherapy for patients with neck and/or shoulder complaints compared to usual physiotherapy.

## Objectives

Our primary research aim is to investigate the clinical effectiveness of the Stratified Blended Approach for patients with neck and/or shoulder complaints on a combined measure of pain and disability over 9 months, compared to usual physiotherapy care.

Our secondary aims are twofold:

- to investigate the effectiveness of the Stratified Blended Approach for patients with neck and/or shoulder complaints on pain intensity, health-related quality of life, illness perceptions, physical activity, self-management skills and self-perceived effect over 3 and 9 months; and exercise adherence and satisfaction at 3 months, compared to usual physiotherapy care;
- to investigate the cost-effectiveness and cost-utility of the Stratified Blended Approach for patients with neck and/or shoulder complaints over 9 months, compared to usual physiotherapy care.

## Trial methods

### Design and randomization

A multicenter, pragmatic, two-arm, parallel-group, cluster randomized controlled trial (cRCT) will be conducted. Physiotherapists will be recruited from primary care physiotherapy practices across all regions of the Netherlands. After recruitment, participating primary care physiotherapy practices will be randomized to either offer the Stratified Blended Approach or usual physiotherapy care by a computer-generated random sequence table generated using SPSS, using 1:1 allocation. The number of physiotherapists per participating practice (dichotomized into '1' and '>1') will be used as a stratification variable. Although individual physiotherapists are identified as clusters, physiotherapy practices will be the unit of randomization in order to prevent contamination between physiotherapists within one practice.

### Sample size

We aim to reach a sample size of 238 patients. The full sample size calculation is provided in the trial protocol.

### Framework

All outcomes are analyzed for superiority of the Stratified Blended Approach arm compared to the usual physiotherapy arm.

### Statistical interim analysis and stopping guidance

Interim analyses are not planned.

### Timing of final analysis

Analyses will take place after locking the database. The database will be locked after the last patient completes the final follow-up questionnaire and after data are checked on outliers and missing data (anticipated December 2023).

### Timing of outcome assessments

The first assessment will consist of a digital questionnaire and an accelerometer that will be sent to the patients by mail and patients will be asked to wear the accelerometer for five consecutive days. Patients will be asked to complete the first questionnaire within one week after starting physiotherapy treatment. Outcomes will be measured again at 3, 6, and 9 months after the first digital questionnaire was completed. Schedule of enrolment, interventions and assessment is provided in our trial protocol (Table 2).

## Statistical Principles

### Confidence intervals and *P* values

All analyses are described in this statistical analysis plan and are therefore considered *a priori* analyses. If applicable, *post hoc* analyses will be identified as such in the articles.

For all analyses, a two-tailed significance level of  $p < 0.05$  is considered to be statistically significant. All confidence intervals presented will be 95% and two-sided. The assumption of normality will be checked with Q-Q-plots and histograms. The interquartile range will be reported for skewed data.

Statistical analysis will be performed using IBM SPSS 27 or statistical package STATA. During the analyses, the researchers will be blinded to group allocation until the entire analysis will be completed.

### Adherence/compliance and Protocol deviations

Compliance to the smartphone app with e-Exercise modules in the Stratified Blended Approach arm will be assessed by quantitative data on the usage. These data will automatically be stored on the backend of the app. Additionally, all patients will be asked in the first follow-up questionnaire whether they received and used an app or paper-based workbook as part of their physiotherapy treatment. Participants will be considered compliant to the e-Exercise modules (app) if they log in once a week in 67% (low risk: 2 weeks over 3 weeks) or 75% (medium/high risk: 9 weeks over 12 weeks) of the total amount of weeks. Participants will be considered to comply to the paper-based workbook if they self-report that they used the workbook at T1 (3 months). Descriptive statistics on the percentage adherent (plus N, mean, SD, median, minimum, maximum) will be summarized per arm.

Because of the pragmatic design of the trial, there are no protocol deviations that might impact the analyses. An overview of the content of physiotherapy sessions & number of physiotherapy sessions will be described for both arms.

[figure not shown]
### Analyses populations

[figure not shown]
All main analyses will be performed according to the 'intention-to-treat' principle. Missing value analyses or imputation will not be performed, because primary analyses will be linear mixed models (LMM).

Additionally, per protocol analyses will be carried out with people that complied to the paper-based workbook or the e-Exercise modules, compared to the control arm.

## Trial Population

Screening data, eligibility, recruitment and loss to follow-up

## Analysis

### Outcome definitions

#### **Effectiveness**

##### *Primary outcome*

- The primary outcome is the combined region-specific pain and disability score over 9 months follow-up, assessed by the Neck Pain and Disability Scale (NPAD) for patients with primarily neck complaints and by the Shoulder Pain and Disability Index (SPADI) for patients with primarily shoulder complaints. A higher total score (0-100 for both outcome measures) indicates increased pain and functional limitations.

##### *Secondary outcomes*

- The average neck and/or shoulder pain intensity in the last week will be measured with an 11-point Numeric Rating Scale (NRS) (0 = no pain; 10 = worst pain imaginable).
- Health-related quality of life will be measured with the 36-Item Short Form Health Survey (SF-36). The questionnaire consists of eight subscales (physical functioning, role limitations due to physical health, role limitations due to emotional problems, energy/fatigue, emotional well-being, social functioning, pain (over the last 4 weeks) and general health). Scores for each subscale will be calculated (0-100). Higher scores indicate a better health-related quality of life.
- Illness perceptions will be measured with the Brief Illness Perception Questionnaire (IPQ-K). This questionnaire is an eight-item scale designed to assess cognitive and emotional representations of illness on an ordinal scale (0-10).
- Patients' self-management skills are assessed with the Dutch version of the short form Patient Activation Measure (PAM13-Dutch). The PAM 13-Dutch is a reliable 13-item instrument and assesses patient (or consumer) self-reported knowledge, skills and confidence for self-management of one's health or chronic condition. The answering categories per item are 4-point Likert scales, ranging from totally disagree to totally agree

and 'non applicable'. A higher score (range 1-100) indicates a higher level of self-management.

- Physical activity will be measured with an Actigraph accelerometer. The Actigraph accelerometer is a reliable tool for measuring physical activity in adults. Participants will be instructed to wear the accelerometer on their waist for five consecutive days, except when sleeping, showering, bathing or swimming. Average amount of moderate or vigorous physical activity (MVPA) per day will be calculated. Data will be eligible if patients had worn the meter at least 3 days, for 8 hours or more. PA thresholds of Freedson et al. were used to distinguish sedentary activity and light, moderate, and vigorous PA. Moderate activity and vigorous activity will be summed and divided by the number of wearing days to calculate a PA score in minutes per day.
- Exercise adherence will be measured with the Exercise Adherence Rating Scale (EARS). The EARS is a 6 item self-reported questionnaire with items scored on a 5-point Likert scale (0 = completely agree; 4= completely disagree). A higher score (0-24) indicates better adherence to prescribed home-exercises. This outcome will not be measured at 9 months follow-up.
- Global perceived effect will be measured with the 7-point Likert global perceived effect score (GPE). Categories 1 (very much improved) to 3 (a little improved) are classified as 'improved'. Categories 4 (no change) to 7 (very much worse) are classified as 'not improved'.
- Satisfaction with treatment outcome will be measured with an 8-point Likert scale question: 'All things considered, how satisfied are you with the results of the treatment for your neck and/or shoulder complaints? (1 = extremely satisfied, 7 = extremely dissatisfied, 8 = not sure/no opinion). This outcome will not be measured at 9 months follow-up.

#### *Demographic and clinical characteristics*

- Patient characteristics are only collected in the first questionnaire and include various demographic and clinical variables, including: age, sex, education level, duration of complaints, weight, height and co-morbidities.
- The risk of persistent disabling pain will be assessed with the Keele STarT MSK Tool (i.e. low, medium or high risk). The Keele STarT MSK Tool is part of the Stratified Blended Approach and is additionally included in the data collection.
- As part of the data collection, patients' suitability for e-Exercise (blended care) will be measured by two self-developed questions as substitute for the Dutch Blended Physiotherapy Checklist. It is not possible to use the Dutch Blended Physiotherapy Checklist as a measurement instrument, because it is a tool to guide physiotherapists in their clinical reasoning while setting up a personalized blended physiotherapy treatment,

thus not a patient reported outcome measure. Therefore, this cannot be measured in the control arm and substitute questions will be used. The following questions will be assessed in the first questionnaire to measure smartphone or tablet access and usage: 'Do you own a smartphone or tablet? (yes/no)' and 'How many apps do you use regularly (weekly) on your smartphone or tablet? (none/1-3 per week/4-10 per week/more than 10 per week)'.

#### *Other outcomes*

- Compliance to the smartphone app with e-Exercise modules in the Stratified Blended Approach arm will be assessed by quantitative data on the usage. These data will automatically be stored on the backend of the app. Additionally, all patients will be asked in the first follow-up questionnaire whether they received and used an app or paper-based workbook as part of their physiotherapy treatment.
- The content and intensity of physiotherapy care will be described from trial case report forms, for both trial arms, filled out by the physiotherapists at the end of the treatment period or after 3 months. Information of the risk of persistent disabling pain, the suitability for blended care, the physiotherapists diagnosis of the presenting problem, the number of physiotherapy sessions, deviations from the study protocol, and content of the physiotherapy sessions will be collected. Number of physiotherapy sessions and content of the physiotherapy sessions will be presented in a table, separately for the 3 risk groups and per trial arm.

#### **Cost-effectiveness**

A cost-utility analysis (CUA) will be performed for QALYs and a cost-effectiveness analysis (CEA) for the combined region-specific pain and disability score, both of which will be performed from the societal (primary outcome) and the healthcare (secondary outcome) perspective. From the societal perspective all costs will be taken into account, irrespective of who pays or benefits, whereas solely those borne by the healthcare sector will be included if the healthcare perspective is applied.

#### **Identification, measurement and valuation of costs**

Societal costs will be determined during 9 months of follow-up by gathering information on the patients' healthcare utilization, informal care, and (unpaid) productivity losses due to neck and/or shoulder complaints. This will be done by asking patients to complete three retrospective 3-monthly cost questionnaires. The costs of the Stratified Blended Approach will be estimated using a bottom-up micro costing approach. Other kinds of healthcare utilization will include the use of primary care, secondary care, and medication, all of which will be assessed by the cost questionnaires and valued using Dutch standard costs. If standard costs are unavailable, prices reported by professional organizations will be used. Unpaid productivity losses will be valued using a Dutch recommended shadow price. Paid productivity losses comprise of both sickness absence and presenteeism (i.e. reduced productivity while at work). Sickness absence will be assessed

using a modified version of the iMTA Productivity Cost Questionnaire (iPCQ) and will be valued in accordance with the “Friction Cost Approach” (FCA), with a friction period of 12 weeks and gender-specific price weights. The FCA assumes that production losses are confined to the “friction period” (i.e. time needed to replace a sick worker). The participants’ level of presenteeism will be measured using the “World Health Organization – Work Performance Questionnaire” as well as a modified version of the iPCQ, and will be valued using gender-specific price weights as well.

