### **Cost-effectiveness**

For the CUA and CEA, missing cost and effect data will be imputed using multivariate imputation by chained equations. The results of the imputed datasets will be pooled using Rubin's rules. LMM, with the same three-level structure as described above, will be performed to estimate cost and effect differences. See the tables below. In order to account for the highly skewed nature of cost data, bias-corrected and accelerated bootstrapping with 5000 replications will be used to estimate 95% confidence intervals around the cost differences. Incremental Cost-Effectiveness Ratios (ICERs) will subsequently be calculated by dividing the differences in costs between trial arms by the difference in QALYs for the CUA and the differences in combined measure of pain and disability for the CEA. The uncertainty surrounding the ICERs will be graphically illustrated by plotting bootstrapped incremental cost-effect pairs on cost-effectiveness planes. Moreover, cost-effectiveness acceptability curves (CEACs) will be constructed to provide a summary measure of the joint uncertainty of costs and effects. CEACs indicate the probability of the Stratified Blended Approach being cost-effective in comparison to usual physiotherapy care at different willingness-to-pay values. To test the robustness of the trial results, several sensitivity analyses will be performed.

**Tabel 3. Mean costs per participant in the Stratified Blended Approach arm and usual physiotherapy (PT) arm and mean differences between both arms during 9 months follow-up**

	SBA (N = ); mean costs in € (SEM)	Usual PT (N = ); mean costs in € (SEM)	Unadjusted mean cost difference in € (95% CI)	Adjusted mean cost difference in € (95% CI)
Intervention a				
Primary healthcare				
Secondary healthcare				
Medication a				
Sport				
Informal care				
Absenteeism				
Presenteeism				
Unpaid productivity				
Healthcare costs b				
Total costs				

aSignificant difference between Stratified Blended Approach and usual PT; bHealthcare costs = intervention costs + primary healthcare costs + secondary healthcare costs + medication costs adjusted for sex, age, BMI, level of education, type of complaints (neck or shoulder), physical functioning at baseline, pain at baseline and utility score at baseline

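### Does the costing plan price physiotherapy differently by arm, or count intervention sessions twice?

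*SAP*

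**What the plan says.** Under the heading on identification, measurement and valuation of costs, the SAP treats the intervention first: "The costs of the Stratified Blended Approach will be estimated using a bottom-up micro costing approach". It then turns to everything else: "Other kinds of healthcare utilization will include the use of primary care, secondary care, and medication", and continues "all of which will be assessed by the cost questionnaires and valued using Dutch standard costs". The instrument is "three retrospective 3-monthly cost questionnaires", which together cover the 9 months of follow-up. If no standard price exists, prices from professional organizations are used.

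The setting is stated under Design and randomization: "Physiotherapists will be recruited from primary care physiotherapy practices across all regions of the Netherlands". Practices are randomized to offer either the SBA or usual physiotherapy, so the treatment under test in both arms is itself primary care.

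Table 3, under Cost-effectiveness, has one row for the intervention and another for primary healthcare. Each row has a column for both arms. Its footnote sums them: "Healthcare costs = intervention costs + primary healthcare costs + secondary healthcare costs + medication costs".

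Under Other outcomes, case report forms record the number and content of physiotherapy sessions in both arms, "filled out by the physiotherapists at the end of the treatment period or after 3 months". They serve to describe the care delivered. The costing section does not name them as a source.

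**The concern.** The Background defines the SBA as physiotherapy whose content, intensity and mode of delivery are matched to the patient. It is not described as an extra laid on top of usual sessions. The costs of the SBA could therefore include its sessions, valued by micro-costing. Usual physiotherapy has no method of its own in the text and could enter only as primary care reported by patients at a standard price. The same kind of contact would then be priced by two methods.

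SBA patients may also report their trial sessions in the cost questionnaires. If nobody removes those reports, the sessions appear in both rows that the Table 3 footnote adds together, and only in the SBA arm.

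Cost-effectiveness and cost-utility are a stated secondary aim. An error here would pass into the cost difference, the cost-effectiveness ratio, the quadrant shares and the acceptability curve, from both the societal and the healthcare perspective. The sensitivity analyses named in Table 4 (complete cases and per-protocol) do not vary the costing method and so would not reveal it.

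**Working it through.** The SAP has no figure to reproduce on this point, so the check starts from the text.

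**The possible readings.** Let *s* be sessions per SBA patient, *u* sessions per usual-care patient, *m* the micro-cost of a session, *p* the standard price, and *a* the cost of what the SBA adds (app, workbook, training).

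1. Micro-costing covers the sessions, and they are kept out of primary healthcare. The difference is *sm* − *up* = (*s* − *u*)*p* + *s*(*m* − *p*). The last term comes from the choice of unit cost.
2. Micro-costing covers the sessions, and they are also left in primary healthcare. The SBA arm is charged *s*(*m* + *p*), an excess of *sp*.
3. Micro-costing covers only the added components. The difference is (*s* − *u*)*p* + *a*. Sessions are valued alike and counted once.

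**Which readings the text supports.**

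- Reading 2 runs against the wording. The questionnaire category opens with the phrase on other kinds of healthcare, directly after the sentence on the SBA. Care delivered as the SBA is thus placed outside it. What is unwritten is only the practical step of applying this to patients' answers.
- Reading 1 is possible, but Table 3 does not require it. The intervention row has a usual-physiotherapy column, so trial physiotherapy in both arms may be entered there by one method. The table is an unfilled shell and weak evidence either way.
- Reading 3 fits the text and produces no artefact.
- The case report forms do not compete as a source. They close at the end of treatment or after 3 months and are descriptive. The questionnaires are the named source for healthcare use.

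**Size, on assumed inputs.** Only the planned sample comes from the SAP: "We aim to reach a sample size of 238 patients", or 238 / 2 = 119 per arm. Everything else is an assumption: 4 to 10 sessions, EUR 30 to 45 per session, a micro-cost 10 to 25% away from the standard price, a healthcare-cost SD of EUR 300 to 600, and a design effect (DE) of 1 to 1.5.

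| | Low | Central | High |
|---|---|---|---|
| Reading 1, *s* × *p* × gap | 4 × 30 × 0.10 = 12 | 6 × 35 × 0.20 = 42 | 10 × 45 × 0.25 = 112.5 |
| Reading 2, *s* × *p* | 4 × 30 = 120 | 6 × 35 = 210 | 10 × 45 = 450 |
| SE = SD × √(2 × DE / 119) | 300, DE 1: 38.9 | 450, DE 1: 58.3 | 600, DE 1.5: 95.3 |

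In the central case reading 1 moves the cost difference by 42 / 58.3 = 0.7 standard errors, up or down, and reading 2 by 210 / 58.3 = 3.6. Across the assumed ranges reading 1 spans 12 / 95.3 = 0.1 to 112.5 / 38.9 = 2.9 standard errors. Reading 2 spans 120 / 95.3 = 1.3 to 450 / 38.9 = 11.6. Reading 3 gives zero. Turning these into probabilities of cost-effectiveness would need an assumed QALY gain, its standard error and a threshold as well, and would add no information.

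**The case for a change.** The strongest case for a change is that the SAP writes its own costing rules and table shells and, unlike for sample size and schedule, does not refer to the protocol for them. Since the SBA is defined as the physiotherapy itself, the plain sense of its costs includes the sessions. Setting SBA care apart in words does not clean questionnaire data, and even where that is done, reading 1 remains open. Blinding of the researchers helps only in part, because costing the SBA may reveal the arm. A few sentences before database lock would close the matter.

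Much of this stands as description. The intervention row is not defined by arm, the scope of the micro-costing is not stated, and no sentence says that each session counts once. It does not show that the plan leads to a wrong result. The large figures all come from reading 2, which needs an analyst to ignore the word that separates the two categories and to add the same sessions twice. Reading 1 yields a false difference only if the true cost of a session is equal in both arms. The SBA changes content, intensity and delivery, so a different unit cost may be real, and imposing one price would remove it. Micro-costing a new intervention while using standard prices elsewhere is a trade-off. Finally, the cost questionnaire is not shown, and whether it asks about trial physiotherapy separately is the kind of detail that an SAP commonly leaves to the instrument or the protocol.

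**Conclusion.** The concern does not call for a change. The SAP leaves a detail of bookkeeping open; it does not prescribe unequal costing or double counting. A health economist filling Table 3 has to decide what the intervention row holds in each arm, and ordinary practice is to count each contact once and to be able to defend the unit cost used. At least one natural reading of the text gives no artefact, and the reading with the largest effect conflicts with the wording.

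The size depends entirely on assumed session numbers, prices and cost variability: nothing under reading 3, EUR 12 to 113 in either direction under reading 1 if true session costs are equal, and EUR 120 to 450 against the SBA under reading 2. The conclusion assumes that the analysts follow the SAP's own separation of SBA care from other care when they process the questionnaires. The matter touches a secondary aim only; the primary effectiveness analysis is unaffected.
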